7.4.4 Vital Signs

For Part A and B, systolic blood pressure, diastolic blood pressure, pulse rate, body temperature, respiratory rate, height (Part B only), and body weight will be summarized as actual values and changes from baseline in the same way as described in Sections 7.1 (Part A) and Section 7.2.1-2 (Part B). Patients<18 years of age in Part B at enrollment will have the modified z-score calculated for their height, weight, and BMI according to CDC growth chart [1].

Separate summaries will be provided in Part B for the single-blind dosing period (by pooled placebo, regimen, and ascending ALN-GO1 dose), the ALN-GO1 dosing period (by regimen and ascending ALN-GO1 dose, regardless of treatment sequence), and the post-dose, safety, and PD follow-up period (by regimen and ascending ALN-GO1 dose, regardless of treatment sequence) as described in Sections 7.2.1-7.2.2.

All vital signs data in Part A and Part B will be listed.

7.4.5 Physical Examinations

For both Part A and Part B, physical examination findings, including any abnormal findings, will be listed. All data from symptom-directed physical examinations will be listed.

For Part B, all data from symptom-related physical examinations will be listed.

7.4.6 ECGs

Analyses of ECGs for both Part A and Part B and will be based on the Safety Analysis Sets.

In Part A, analyses will be presented separately for the single-blind dosing period and safety and PD follow-up period. In Part B, analyses will be presented separately for the single-blind dosing period (by pooled placebo, regimen, and ascending ALN-GO1 dose), ALN-GO1 dosing period (by regimen and ascending ALN-GO1 dose, regardless of treatment sequence), quarterly open-label ALN-GO1 dosing period (by ascending ALN-GO1 dose), postdose follow-up period (by ascending ALN-GO1 dose), and Safety and PD follow-up period (by regimen and ascending ALN-GO1 dose, regardless of treatment sequence).

Subjects with the following diagnoses or abnormal ECG findings will be excluded from the ECG analysis: artificial pacemaker (recorded as presence of atrial pacing, ventricular pacing, and/or atrial ventricular pacing), atrial fibrillation (or flutter), left bundle branch block (complete or incomplete), and right bundle branch block (complete or incomplete).

The number and percentage of patients with normal, abnormal, and clinically significant abnormal results at baseline and each timepoint will be summarized.

For both Part A and Part B, electrocardiogram parameters (ventricular rate, PR, QRS, QT, QT_cB, and QT_cF) will be summarized using descriptive statistics for actual values and for changes from baseline by scheduled time of evaluation (given in the Schedule of Assessments). These summaries will be presented separately for the time periods in Sections 7.1 (Part A) and Sections 7.2.1-2 (Part B).

Baseline, post baseline maximum QTcF, and post baseline maximum change from baseline in QTcF during the study will be summarized with descriptive statistics. The incidence of notable ECG changes from baseline in maximum absolute QT, QTcF, and QTcB intervals (<=450, > 450, > 480, and > 500 ms) over all post-treatment evaluations, as well as in QT, QTcF, and QTcB maximum changes from baseline (> 30 and > 60 ms) over all post-treatment evaluations will be summarized by dose level of ALN-GO1, pooled placebo, and overall for all subjects receiving ALN-GO1 in Part A. In Part B, the summary will be presented by regimen and ascending ALN-GO1 dose level, regardless of treatment sequence.

Scatterplots of QT Interval by RR Interval, QTcF Interval by RR Interval, and QTcB Interval by RR Interval will be presented for the pooled placebo and by regimen and by dose groups. For each QTcF Interval that has a time-matched pharmacokinetic concentration, a scatterplot of change from baseline QTcF Interval by concentration will be presented for the pooled placebo and by regimen and by dose groups. The line produced from simple linear regression will be used as a line of reverence.

A listing of all ECG data will be provided.

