8.2.7. Safety Analyses

The primary safety parameter is the incidence of AEs. Safety will also be evaluated through vital signs, ECGs, clinical laboratory assessments, and physical examinations; Echo assessments will be evaluated in Part B only. ADAs will also be analyzed.

AEs will be summarized by the MedDRA System Organ Class and Preferred Term (Version 16, or higher). Prior and concomitant medications will be classified according to the World Health Organization (WHO) drug dictionary.

Separate tabulations of the incidence of treatment emergent adverse events (TEAEs), TEAEs by maximum severity, treatment-related AEs, SAEs, and discontinuation due to AEs will be provided. By-subject listings will also be provided for any deaths, SAEs and AEs leading to discontinuation.

Descriptive statistics will be provided for clinical laboratory data and vital signs data, presented as both actual values and changes from baseline over time. Clinical laboratory assessment shift tables from baseline to worst post-values will be presented. Abnormal physical examination findings, ECG, and Echo (Part B only) data will be presented in a by-patient data listing.

Descriptive statistics will be provided for ECG interval data and presented as both actual values and changes from baseline relative to each on-study evaluation and to the last evaluation on study. Details of any abnormalities will be included in patient listings.

ADA results will be provided in a by-patient data listing.

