4.3.1 Baseline Definition

The baseline value is defined as the last non-missing value before the first dose of the randomized study drug, unless otherwise specified.

In Part B, for patients who are randomized initially to placebo, the baseline value for the placebo dosing period is defined as the last non-missing value before the first dose of placebo. For these patients, their baseline value for the open-label ALN-GO1 period is defined as the last non-missing value before the first dose of ALN-GO1.

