6.1.5 Electrocardiograms (ECGs)

For both parts A and B, triplicate 12-lead ECGs will be measured 5 minutes apart at times indicated in the Schedule of Assessments. Recording will be obtained after the subject has rested comfortably in the supine position for approximately 10 minutes. ECGs should be performed at approximately the same time of day throughout the study. The Investigator (or designee) is responsible for reviewing ECGs and to determine the clinical significance of the results. The overall interpretation of the ECG will be recorded and any abnormality specified. The Investigator will provide a determination regarding the change from baseline ECG and specification of the change. The electrophysiological parameters assessed will include

- Rhythm
- Ventricular rate
- PR interval

- QRS duration
- QT interval
- ST and T waves
- Bazett-corrected QT interval (QTcB)
- Fridericia-corrected QT interval (QTcF)

All triplicate ECG measurements at a particular time point will be averaged prior to analysis and summarization.

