7.2.3 By-visit Data Presentation

In Part B, the by-visit PD and safety summaries will be presented according to the specifications below.

Monthly Dosing Regimen: Part B

Timepoint ^a	Placebo ^b	Monthly	Monthly	Monthly	Monthly	Monthly	Monthly
	(N=4)	ALN-GO1	ALN-GO1	ALN-GO1	ALN-GO1	ALN-GO1	ALN-GO1
		Single-blind ^c	Comb.d	Single-blind ^c	Comb.d	Single-blind ^c	Comb.d
		Dose1	Dose1	Dose2	Dose2	Total	Total
		(N=3)	(N=4 or 8)	(N=3)	(N=4 or 8)	(N=6)	(N=8 or 16)
Baselinee							
Day 29							
Day 57							
Day 85 ^f							
Day 113	NA						
Day 141	NA						
Day 169 ^g	NA						
Day 197 ^h	NA						
Day 225	NA						
Day 253	NA						
Day 281	NA						
Day 309	NA						

- a: In monthly dosing regimen, patients randomized to ALN-GO1 will be summarized by study day 1 to 85 during the single-blind monthly treatment period, then by post dosing follow-up period after Day 85 and up to Day 169, followed by Safety and PD follow-up after Day 169. Patients randomized to Placebo will be summarized by study day 1 to 85 relative to placebo dosing date during the single-blind treatment period. Data collected after the first dose of ALN-GO1 will be summarized separately by days relative to the first open-label ALN-GO1 dose with all visits for the rest of the study mirrored to the patients randomized to the single-blind ALN-GO1. These data will be summarized in combination with data from patients randomized to ALN-GO1 at each corresponding visit.
- b: Patients from all monthly and quarterly dosing cohorts randomized to placebo at study start
- c: Patients randomized to ALN-GO1 at study start receiving ALN-GO1 in single-blind manner
- d: Patients receiving ALN-GO1 in single-blind or open-label manner and in any sequence combined
- e: Baseline is defined as before first dose date/time of each treatment, placebo or ALN-GO1
- f: Day 85 is the end of treatment period
- g: Day 169 is the end of post-treatment follow-up period
- h: Day 197 and later visits are Safety and PD follow-up visits

Quarterly Dosing Regimen: Part B

Timepointa	Placebob	Quarterly	Quarterly	Quarterly	Quarterly	Quarterly	Quarterly	Quarterly	Quarterly	Quarterly
	(N=4)	2-doses ^c	1-dose ^d	Comb.e	2-doses ^c	1-dose ^d	Comb.e	2-doses ^c	1-dose ^d	Comb.e
		ALN-GO1	ALN-GO1	ALN-GO1	ALN-GO1	ALN-GO1	ALN-GO1	ALN-GO1	ALN-GO1	ALN-GO1
		Dose1	Dose1	Dose1	Dose2	Dose2	Dose2	Total	Total	Total
		(N=3)	(N=1)	(N=4)	(N=3)	(N=1)	(N=4)	(N=6)	(N=2)	(N=8)
Baselinef										
Day 29										
Day 57										
Day 85g										

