9 CHANGES FROM THE PROTOCOL SPECIFIED STATISTICAL ANALYSIS

No changes have been issued or planned.

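### SAP 7.4.6 drops whole subjects with pacing, AF/flutter or bundle branch block from the ECG analysis, even when the finding first appears after dosing

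*SAP*

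**What the plan says.** SAP 7.4.6 bases the ECG analyses on the Safety Analysis Set, which SAP 4.2.1 defines as everyone dosed. It then qualifies this: "Subjects with the following diagnoses or abnormal ECG findings will be excluded from the ECG analysis: artificial pacemaker", followed by atrial fibrillation or flutter and left or right bundle branch block, complete or incomplete. The next sentence sets up the categorical table: "The number and percentage of patients with normal, abnormal, and clinically significant abnormal results at baseline and each timepoint will be summarized". The interval statistics, the QT/QTc outlier tables and the scatterplots come after it. The section ends with a separate commitment: "A listing of all ECG data will be provided".

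Four other places bear on the point:
- **SAP 6.1.5:** "All triplicate ECG measurements at a particular time point will be averaged prior to analysis and summarization". Each parameter therefore has one value per time point.
- **SAP 4.3.1:** Part B placebo patients have a baseline before placebo and a second one later: "their baseline value for the open-label ALN-GO1 period is defined as the last non-missing value before the first dose of ALN-GO1".
- **SAP 7.2.3:** the combined columns hold "Patients receiving ALN-GO1 in single-blind or open-label manner and in any sequence combined".
- **Protocol 8.2.7:** "Descriptive statistics will be provided for ECG interval data and presented as both actual values and changes from baseline". It also sends ECG abnormalities to by-patient listings. It states no exclusion of subjects.

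**The concern.** The rule presumably exists because intervals measured in these rhythms are hard to interpret, although neither document gives a reason. As worded it reaches further in two ways.

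First, it has no time limit. It applies equally to a block present at screening and to one that first appears after the first dose. In the second case the safety summary loses a subject because of a safety finding.

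Second, it is not confined to intervals. The categorical table exists to count abnormal ECGs, and doubts about interval measurement do not affect whether a tracing is abnormal. Yet the table falls under the same exclusion. A group in which one of these findings arose can therefore show no abnormal ECG.

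**Working it through.** The plan states no figure on this point, so there is nothing to reproduce. The check is a reading of the text, followed by counting on planned group sizes.

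**Does anything narrow the rule?** SAP 7.4.6 refers to subjects, not recordings or parameters, and gives no time point. I found nothing in SAP 4.2.1, 4.3.1, 6.1.5 or 7.2, or in protocol 7.5.4 or 8.2.7, that limits it to baseline findings or interval values. Only the listing is expressly for all ECG data.

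**Effect of one new-onset case on the categorical table.** Inputs:
- Part A: 8 per cohort at 3:1 (SAP 3.1.1), so 8 × 3/4 = 6 active.
- Part B: 4 per cohort at 3:1 (SAP 3.1.2), so 4 × 3/4 = 3 active.
- Combined monthly dose group N = 4 or 8, and pooled placebo N = 4 (SAP 7.2.3 table).

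With one case rated abnormal in a group of n, the observed result is 1/n. The rule as written shows 0/(n − 1).

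| Group | Observed | As written |
|---|---|---|
| Part B single-blind dose group | 1/3 (33.3%) | 0/2 |
| Part B combined monthly, N = 4 | 1/4 (25.0%) | 0/3 |
| Part B combined monthly, N = 8 | 1/8 (12.5%) | 0/7 |
| Part A dose group | 1/6 (16.7%) | 0/5 |
| Part B pooled placebo (case arising on placebo) | 1/4 (25.0%) | 0/3 |

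In the last row the same patient also leaves the combined ALN-GO1 column of that cohort, so N = 4 becomes 3.

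**Analysed values lost per parameter.** SAP 7.2.1 starts the Part B single-blind summaries at the first dose, and SAP 4.3.1 makes baseline one value. The three pre-dose ECG time points (screening, Day −1, Day 1 predose) therefore yield one baseline value. I treat Part A in the same way.
- *Part B monthly through Day 85* (protocol Table 2, footnote h): Day 1 at 1, 2 and 4 h = 3; Day 2 = 1; Day 29 = 4; Day 57 = 4; Day 85 = 1. Post-dose total 3 + 1 + 4 + 4 + 1 = 13. With baseline, 13 + 1 = 14.
- *Part A through Day 57* (protocol Table 1, footnote i): Day 1 at 1, 2, 3 and 4 h = 4; Day 2 = 1; Day 29 = 1; Day 57 = 1. Post-dose total 4 + 1 + 1 + 1 = 7. With baseline, 7 + 1 = 8.

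A finding first seen at the last of these visits affects one value. The rule removes all 14 (or 8). Omitting only the affected value keeps 14 − 1 = 13 (or 8 − 1 = 7).

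**The case against.** The best defence is that the sentence was meant for conditions present before dosing. Protocol 5.2.1 bars only clinically significant ECG abnormalities, so a minor block can be present at entry, and the separate programming specification (SAP 8.2), which is not available here, may apply the rule that way. Protocol 8.2.7 promises listings for ECG abnormalities, and the SAP provides one. The categorical table is an SAP addition, and in groups of 3 to 6 a listing can be read in full. Clinically relevant ECG changes are recorded as AEs (protocol 7.5.7.2) and tabulated (SAP 7.4.1). Investigators and the Safety Review Committee are unblinded.

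Most of this stands and limits the weight of the point. It does not repair the wording. The baseline-only reading is not written, and even under it the subject leaves the categorical table for no measurement reason.

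Four stronger readings are tempting and should not be drawn:
- **That a new cardiac finding would vanish from the report.** It stays in the listing and, if clinically relevant, in the AE tables. Only a finding judged not clinically relevant would appear in the listing alone.
- **That this is an undeclared departure from the protocol**, given SAP Section 9: "No changes have been issued or planned". Protocol 8.2 leaves implementation to the SAP, and omitting unsuitable interval values can fairly be seen as implementation.
- **That SAP 7.4.6 contradicts its own use of the Safety Analysis Set.** It is a general rule followed by a qualification that is too broad.
- **That 16 values (Part B monthly) or 10 (Part A) are lost**, counting every scheduled ECG (13 + 3 and 7 + 3). The three pre-dose time points supply only one analysed baseline value.

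**Conclusion.** The point holds on the text. Applied as written, SAP 7.4.6 conditions the ECG summary tables on a post-dose safety finding and can show no abnormal ECG in a group that had one. The size is that of a single case in a very small group: 1/3 to 0/2 in Part B, 1/6 to 0/5 in Part A, with up to 14 or 8 analysed values per parameter lost when one is affected.

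These figures assume one new-onset case, rated abnormal, at planned group sizes. The documents give no frequency, and it may be zero. The rationale for protocol Amendment 3 reports no signs or symptoms of cardiac abnormalities in preliminary Part A data, although that may not cover an asymptomatic block. The consequence is confined to descriptive ECG summaries, and the primary endpoint, AE incidence, is unaffected. I rate it between minor and should-fix: the effect is small, but the rule gives a wrong safety summary when followed and is cheap to correct.

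**What to change.** Replace the exclusion sentence in SAP 7.4.6 with four statements:

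1. All Safety Analysis Set subjects stay in the normal/abnormal/clinically significant table.
2. The exclusion applies only to a named list of interval parameters (such as PR, QRS, QT, QTcB and QTcF) and to the outlier tables and scatterplots built on them.
3. A subject's interval values are omitted throughout only if the finding is present at the SAP 4.3.1 baseline. That is the last value before the first dose of randomised drug or, for the ALN-GO1 period of a placebo patient, before the first ALN-GO1 dose. For patients randomised to quarterly ALN-GO1 it remains the Day 1 baseline. Using Day 85 predose would relabel a finding that arose after the first ALN-GO1 dose as pre-existing. In all other cases, values are omitted only from the time point at which the finding is first present, and earlier values are kept.
4. The numbers of subjects and values omitted are footnoted by group.

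The cost is SAP wording, footnotes and a little more programming, since exclusion status becomes specific to time point and treatment period. The interval summaries remain partly conditioned on the finding. In particular, a case arising on placebo still loses its interval values in the combined ALN-GO1 columns, though it now stays in the categorical table. The footnote discloses this.

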8.2. Statistical Methodology

A Statistical Analysis Plan (SAP) will be finalized before database lock. The plan will detail the implementation of all planned statistical analyses in accordance with the principal features stated

in the protocol. Any changes to the methods described in the final SAP will be described and justified as needed in the clinical study report.

Statistical analyses will be primarily descriptive. Analyses will be performed using SAS[®] (Version 9.2, or higher). Data from Parts A and B will be analyzed separately. Tabular summaries will be generated by dose level and dosing regimen of ALN-GO1 and placebo (pooled across all cohorts) for Part A and Part B (through Day 85).

Safety and PD data will be summarized by dose level and dosing regimen of ALN-GO1 compared to placebo for data collected up to, and including, study Day 85. Data from placebo patients from all cohorts will be combined. Data collected after Day 85 will be summarized separately for patients in quarterly dosing cohorts who receive a second dose of ALN-GO1 on Day 85. Additionally, all safety and PD data collected from all patients in Part B during the ALN-GO1 dosing period, regardless of treatment sequence, will be combined and summarized by ALN-GO1 dose level and regimen.

Data collected beyond the designated dosing period will be summarized or presented in data listings.

Descriptive statistics will be presented for continuous variables. Frequencies and percentages will be presented for categorical and ordinal variables. Percentages will be based on the number of non-missing values in a dose group.

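### The SAP sentence on the Part B notable-QT/QTc table names no placebo group, which conflicts with the opening rule of its own section and with protocol 8.2

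*SAP*

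**What the plan says.** SAP 7.4.6 counts patients by maximum absolute QT, QTcF and QTcB (categories at 450, 480 and 500 ms) and by "maximum changes from baseline (> 30 and > 60 ms) over all post-treatment evaluations".

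- **Part A grouping:** the table "will be summarized by dose level of ALN-GO1, pooled placebo, and overall for all subjects receiving ALN-GO1 in Part A".
- **Part B grouping:** "In Part B, the summary will be presented by regimen and ascending ALN-GO1 dose level, regardless of treatment sequence".
- **Opening rule of the same section:** "In Part B, analyses will be presented separately for the single-blind dosing period (by pooled placebo, regimen, and ascending ALN-GO1 dose"). The rule then lists the ALN-GO1 dosing period and the later periods without placebo.
- **Protocol 8.2, Part B:** "Safety and PD data will be summarized by dose level and dosing regimen of ALN-GO1 compared to placebo for data collected up to" and including Day 85. The same paragraph also provides for a combined summary of all ALN-GO1 data by dose and regimen, whatever the sequence.
- **Protocol 8.2.7:** "Descriptive statistics will be provided for ECG interval data and presented as both actual values and changes from baseline". It does not ask for outlier categories.
- **SAP Section 9:** no change from the protocol's analyses is declared.

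**The concern.** The Part B sentence uses nearly the same grouping phrase that the opening rule gives to the ALN-GO1 dosing period, which has no placebo group. A programmer who follows the specific sentence would build the table without placebo.

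The other main Part B safety tables keep placebo for the single-blind period: adverse events (SAP 7.4.1), laboratory shifts (7.4.3), vital signs (7.4.4) and clinically significant echocardiographic changes (7.4.7).

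The statistic makes the gap more awkward. A per-patient maximum rises with the number of readings even without a drug effect, so a count of changes above 30 ms needs a reference group observed over the same window. The Part B table runs over all post-treatment evaluations, while placebo patients are on placebo only until about Day 85. A placebo column simply set beside the present table would therefore compare unequal windows.

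**Working it through.** **1. How many placebo patients there are.** SAP 3.1.2 gives cohorts of 4 randomized 3:1, so 1 placebo patient per cohort. The shells in SAP 7.2.3 show two monthly and two quarterly dose levels: 4 cohorts × 1 = 4, which reproduces the N=4 printed there. Two planned plus three optional cohorts would give 5. The protocol synopsis mentions up to 6 sequential cohorts, which would give 6 if all were randomized.

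**2. How many ECG times fall in the window** (protocol Tables 2 and 4, ECG row and footnote h; post-dose ECGs at 1, 2 and 4 hours on dosing days).

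- Monthly, through Day 85: Day 1 (3), Day 2 (1), Day 29 (4, with predose), Day 57 (4), Day 85 (1) = 13. Days 113, 141 and 169 bring it to 16.
- Quarterly, through the Day 85 predose ECG: Day 1 (3), Day 2 (1), Days 29, 57 and 85 (1 each) = 7. Day 85 postdose (3) and Days 86, 113, 141 and 169 bring it to 14.

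**3. Chance of at least one change above 30 ms with no drug effect.** The documents give no SD, so SDs of 10, 12 and 15 ms for the change are assumed. With m independent readings, P = 1 − (1 − p)^m, where p = P(Z > 30/SD): 0.00135, 0.00621 and 0.02275.

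| Window | m | SD 10 | SD 12 | SD 15 |
|---|---|---|---|---|
| Quarterly to Day 85 predose | 7 | 0.9% | 4.3% | 14.9% |
| Monthly to Day 85 | 13 | 1.7% | 7.8% | 25.9% |
| Quarterly to Day 169 | 14 | 1.9% | 8.4% | 27.5% |
| Monthly to Day 169 | 16 | 2.1% | 9.5% | 30.8% |

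Changes within a patient share a baseline, so independence overstates these figures. With an assumed common correlation of 0.5 (multivariate normal), 13 readings give 1.4%, 5.3% and 15.5%, and 7 readings give 0.8%, 3.4% and 10.6%. Even so, the background is not zero and it grows with the window.

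**4. What a placebo column can show.** With 0 outliers among n placebo patients, the two-sided 95% exact upper limit is 1 − 0.025^(1/n): 60% for n=4, 52% for n=5, 46% for n=6. If the true background were 5%, 10% or 20% per patient (assumed), the chance of at least one outlier among 4 is 1 − (1 − rate)^4 = 19%, 34% or 59%.

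**The case against.** The strongest reply is that placebo has not been dropped. The opening rule of 7.4.6 can be read to govern every Part B ECG analysis, SAP 4.3 makes placebo a default column, and the all-ALN-GO1 grouping has its own basis in protocol 8.2. This stands in part: the fault is an inconsistency between two sentences rather than a proven omission, and the existing display is legitimate. But the specific sentence still needs reconciling with the rule.

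A reader might also infer that, without this column, QTc outliers on drug cannot be told from background. The documents do not support that:

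- The interval summaries follow the periods of SAP 7.2.1–7.2.2, and 7.2.1 pools placebo. SAP 4.3 adds the minimum and maximum, so they show whether any placebo patient crossed a threshold at a scheduled time.
- The QT-versus-RR plots include pooled placebo, and "a scatterplot of change from baseline QTcF Interval by concentration will be presented for the pooled placebo and by regimen and by dose groups".
- All ECG data are listed.

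What these outputs lack is a count of distinct placebo patients by maximum over the window. With about 4 patients that count can be made by hand from the listing. Nor would the added column settle causation, as the 60% limit shows; SAP Section 7 rules out formal testing.

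**Conclusion.** The point holds as a minor inconsistency. The Part B sentence differs from the Part A sentence, from the lead rule of its own section and from protocol 8.2, and SAP Section 9 declares no departure. The consequence is one safety table without its natural reference group, in a descriptive study that reports placebo QTc elsewhere.

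The chance-exceedance figures only illustrate why the window matters. They rest on assumed SDs, normal changes and, in the main table, independent readings. Realistic values are likely lower, because readings within a patient are correlated and quarterly patients have fewer of them. That the sentence names no placebo group follows from the text alone and does not depend on these assumptions.

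**What to change.** In SAP 7.4.6, replace the Part B sentence with two displays of the notable-QT/QTc table:

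- **(a)** the single-blind period through Day 85, by pooled placebo, regimen and ascending ALN-GO1 dose;
- **(b)** all ALN-GO1 exposure by regimen and dose regardless of sequence, as now.

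End display (a) at the Day 85 predose ECG in every group. SAP 7.2.1 otherwise includes all of Day 85 for patients randomized to ALN-GO1 but stops before the first active dose for placebo patients. In quarterly cohorts that would add three postdose readings on the active side only.

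Apply the same split to the summary of maximum QTcF and its maximum change, for which the section states no grouping. Add a note that the placebo column is for descriptive context.

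The cost is a short SAP edit and one extra table from ECGs already scheduled. No new data are needed.
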